Another issue is confidentiality, but we will take all possible steps to maximize confidentiality. None of the personal information that we collect will be shared with Twitter group members or anyone outside the research staff except for the names and photos provided by the participants will be displayed to their Twitter group. Each participant will be given a secure login identity and password, with a unique ID which will be used by researchers to track individuals. No names will be on the surveys or datasets, and the list of identifying links will be available only to the research staff. The researchers will make every possible effort to ensure that no one except research staff will see the completed surveys.

In addition, there are some confidentiality issues that may apply to interactive peer messaging groups. First, members of the interactive peer messaging groups will know their group members' Twitter user names and real names, and they will see the groups' messages that are sent to all members, as well as the individual messages that are sent just to them, because they will be interacting with each other on Twitter. They will see participants' profile photos on Twitter as well as participants' names so that they can better interact with each other. Further, members of the interactive peer messaging groups could decide to voluntarily share personal identifying information with other group members, or even call or meet other members in person. However, this risk is no greater than if they were regular participants on Twitter.

Ethical Reporting

If there is indication of child abuse, neglect, or homicidal actions, we will report participants to the necessary authorities. Name and contact information will be given to the appropriate authorities to ensure the safety of the participant and those around them, based on the participant's tweets and emails. This will only be done if the participant's life or anyone else's life is in danger as we want to protect the confidentiality of the participant when at all possible.

Nicotine Replacement Therapy

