This is an NIH funded/supported study and a CoC will be automatically issued for studies that involve identifiable, private, and sensitive information.

2. Explain in what situations the UCI study team will disclose identifiable private information protected by a CoC.

Researchers will disclose identifiable information under the following circumstances: Tweets will be monitored to ensure safety of all participants. If any tweets indicate child abuse, neglect, or homicidal intent we are legally obligated to report the messages. If any tweets indicate suicidal thoughts, we will refer the subject to the appropriate mental health services.

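### The danger-to-life limit on reporting in Section 7.B conflicts with that paragraph's own opening sentence and with the unconditional reporting duty in Section 10.E

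*Protocol*

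**What the plan says.** Two places in the protocol state when staff will act on alarming content from a participant.

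**Protocol Section 7.B, Risks and Discomforts, Ethical Reporting paragraph.** It opens with a commitment: "If there is indication of child abuse, neglect, or homicidal actions, we will report participants to the necessary authorities". It then says what is passed on and why: "Name and contact information will be given to the appropriate authorities to ensure the safety of the participant and those around them". The signal is described as "based on the participant's tweets and emails". The closing sentence sets a limit: "This will only be done if the participant's life or anyone else's life is in danger". The reason given for the limit is to preserve confidentiality as far as possible. Suicidal content is not named.

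**Protocol Section 10.E, Certificate of Confidentiality, item 2.** The answer is introduced by "Researchers will disclose identifiable information under the following circumstances". It says that tweets are monitored for participant safety and then gives two rules. The first is "If any tweets indicate child abuse, neglect, or homicidal intent we are legally obligated to report the messages". The second is "If any tweets indicate suicidal thoughts, we will refer the subject to the appropriate mental health services". Neither carries a danger-to-life condition.

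A third rule is related. Section 6.A, under Initial Pilot Groups, says that a Twitter member whose inappropriate behavior persists or is extreme, with threatening behavior as the example, will be discontinued and given other quit-smoking referrals. It says nothing about reporting.

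**The concern.** The word "only" in the closing sentence of the Ethical Reporting paragraph is an explicit restriction. Read literally, it takes back part of what the paragraph's first sentence promises, and part of what Section 10.E calls a legal obligation. Neither section refers to the other or says which governs.

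Section 10.E says that tweets are monitored, so staff are expected to see such messages and act on them. If abuse or neglect is indicated and no life is threatened, a staff member who applies the Section 7.B limit omits a report that Section 10.E describes as legally required. One who applies Section 10.E discloses identity in a case where Section 7.B says it will be protected. What is at stake is participant and third-party safety and the stated limit of confidentiality, not the validity of the trial's comparisons.

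**Working it through.** No figure in the plan bears on this point and no calculation applies. The check sets the two texts side by side.

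**Elements of each rule**

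- Triggers. Section 7.B: child abuse, neglect, homicidal actions. Section 10.E: child abuse, neglect, homicidal intent and, separately, suicidal thoughts.
- Threshold. Section 7.B: the participant's or another person's life is in danger. Section 10.E: none beyond the content being indicated.
- Action. Section 7.B: report the participant, with name and contact information, to authorities. Section 10.E: report the messages; for suicidal thoughts, refer to mental health services.
- Sources. Section 7.B: tweets and emails. Section 10.E: tweets.

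**Case by case**

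1. *Abuse, neglect or homicidal content in a tweet, with a life in danger.* The Section 7.B trigger and its limit are both met, so it says report. Section 10.E also says report. The two agree.

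2. *Abuse or neglect in a tweet, with no life in danger.* The first sentence of the Section 7.B paragraph says report, and its last sentence rules that out. Section 10.E says report. The limit therefore contradicts both its own paragraph and Section 10.E. This is the direct clash.

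3. *Suicidal thoughts in a tweet.* Section 10.E says refer. It places that rule under an introduction about disclosing identifiable information, without saying what would be disclosed or to whom. Section 7.B does not name suicidal content, but its purpose includes the participant's own safety and its limit mentions the participant's life, so it can be read as reaching such a case. The result is an unclear overlap, not two opposed instructions.

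4. *The same content in an email.* Section 7.B covers it and Section 10.E is silent. This is a difference in scope, and nothing in Section 10.E contradicts Section 7.B here.

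5. *Threatening content toward the group.* The Section 6.A rule deals with membership and referral. It does not set a reporting threshold, so it does not settle case 2, but it may apply to the same message as the homicidal trigger.

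Of the five cases, one is a contradiction (case 2), one is an unclear overlap (case 3), one is a scope difference (case 4), one shows agreement (case 1), and one is a neighboring rule to check for consistency (case 5).

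**The case against.** The strongest reply is that the two sections largely say the same thing. Their triggers are almost identical, both commit to reporting, and they agree whenever a life is in danger. The limiting sentence ends with a confidentiality rationale, so it can be read as a general preference that yields to any legal duty. On that reading the paragraph is clumsy but workable.

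Much of this stands. A reader might infer that the two sections give opposite instructions for the same message; the documents do not support that, because Section 7.B itself says that these triggers will be reported. A reader might also infer that suicidal content is to be referred and nothing more. Section 10.E does not exclude further action, and it lists the referral among circumstances of disclosure. Nor does the difference over emails amount to a conflict.

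A further tempting step is to size the problem by enrollment, for example the 480 + 240 = 720 planned Twitter participants in Section 1. That counts people whose tweets may be seen, not messages on which the rules disagree. It would also be too strong to say that no other rule touches such content, given Section 6.A.

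The softer reading does not remove case 2. The limit is worded as an exclusive condition, and nothing in the paragraph makes it subordinate to Section 10.E or to a legal duty. Staff would have to supply that reading themselves.

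**Conclusion.** The point holds in a narrow form. The danger-to-life limit in the Ethical Reporting paragraph conflicts with that paragraph's opening sentence and with the unconditional duty stated in Section 10.E. The direct clash is confined to abuse or neglect indicated without danger to life. The treatment of suicidal content is not aligned between the two sections, and the sources they cover differ.

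The documents give no expected number of such messages, so no rate is claimed. The conclusion rests on the wording alone. It takes the protocol's own description of the duty as legal at face value and makes no independent claim about the law. The consent pages are not available for review, so nothing is said about what participants are told. Endpoints, sample size and analysis are unaffected. The correction is still worth making, because following one stated rule would breach a duty that the protocol elsewhere calls legal.

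**What to change.** Reconcile the Ethical Reporting paragraph of Section 7.B with Section 10.E item 2, and check both against the Section 6.A rule on threatening behavior. The result should be one statement of triggers, threshold, action and sources, used in the same form in both places. It should make clear how suicidal content is handled and whether that involves disclosure of identity. This review does not say which rule is right; that is for the investigators and the IRB to decide.

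The cost is protocol wording and an IRB modification. Nothing changes in the sample, the outcome measures or the statistical analysis plan.

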## Tweet2Quit Statistical Analysis Plan

## Statistical Analyses

Dropout rates are examined by condition. Every effort is made to limit the amount of missing data from survey attrition by doing persistent follow-up with participants and contacting their preidentified collaterals (family members and friends) to urge survey completion. Before analysis, we will examine baseline predictors of attrition. If it appears that attrition is related to measured aspects of the participants, we will include those measures as covariates in the models. Sensitivity analyses will check that the methods of dealing with missing data do not have a major impact on the results. We will repeat the attrition analyses under 2 different models, one in which the missing data are assumed to be positive for smoking and one using only the respondents who did not have missing data. We expect to find that although estimates may change some, the conclusions generated by the modeling should not change.

For primary hypothesis testing of sustained abstinence at 6 months, we will use the 6-month post quit date survey (based on the quit date selected by the participant at the beginning of the study) and biochemical salivary cotinine verification. To test the *primary aim 1 hypothesis*, analyses will compare sustained abstinence for participants randomized to coed Tweet2Quit treatment versus control. Sustained abstinence will be modeled as a function of study arm (coed Tweet2Quit or control), gender, cohort, and individual using a logistic model and generalized estimating equations (Proc Genmod in SAS) to account for the clustering of individuals within cohort. Our statistical methods will use all the data in parameter estimation. We will test the coefficient of the study arm or treatment condition parameter, doing so by gender if there is a treatment condition by gender interaction.

The same type of generalized logistic model, but focusing on women, will be used to test the *primary aim 2 hypothesis*, on whether women will achieve greater 6-month sustained, bioconfirmed abstinence if randomized to a women-only versus coed Tweet2Quit treatment group. Secondary hypotheses concerning sustained abstinence at 3 months (ie, at treatment end) and point prevalence (prior 7 day) abstinence at 1, 3, and 6 months will be tested using the same modeling approaches.

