In Years 2-5, we will achieve Aim 1 and 2: to conduct a 3-arm cluster-randomized controlled trial of the 2nd generation *Tweet2Quit* Twitter-delivered group intervention. Both treatment (coed and women only) and control participants will receive a web-based quit plan referral, 8-weeks of nicotine patches and 8-weeks of nicotine gum/lozenges but the control groups will get this without Twitter support. Cohorts of 20-30 smokers that have passed the screening will be randomly assigned to treatment coed (with control) or treatment women only and then treatment participants will be grouped into demographically homophilous dyads or buddy pairs. Thus, both dyads and cohorts will be nested factors in the analyses.

Although UCI is collaborating with UCSF, Investigator [name] is not engaged in human-subjects research, given he is not interacting with participants, and he is not accessing identifiable data. UC Reliance #977 is *inactive*

Recruiting is a continuous ongoing activity and a new group is created once 20-30 applicants have completed the enrollment process. [name] will create a randomization table that will determine, e.g., every month, if the next cohort to be recruited will be coed or women-only, with 2/3rds of the cohorts being

coed and 1/3rd being women-only. A coed cohort of 30 smokers will have a minimum of 6 men (max. 10) and a maximum of 24 women (min. 20). Then, [name] will randomize 20 of these smokers to coed treatment and 10 smokers to coed control with the provisos that there be (a) a minimum of 4 men in coed tweet2quit (to ensure a critical mass), and (b) even numbers of men and even numbers of women in coed tweet2quit, i.e., 4, 6 or 8 not 3, 5 or 7 (for buddy pairing within gender). [name] will not see any identifiable subject data; he will only see anonymized subject numbers such as G01P01. If the treatment cohort to be recruited is women-only, then only women will be recruited. Any men that we also recruit will be waitlisted and placed in the next coed cohort. As treatment to control ratios of genders may not be equivalent, gender will be taken into account as a covariate during analysis.

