In addition, participants will complete a contact form which will ask for their name, mobile phone, home and/or work phone if applicable, home mailing address (to get the nicotine patches and nicotine gum/lozenges), email address (to get survey links), Facebook URL or Social Media picture (to validate they have a social media account), identifying photo (to post on Tweet2Quit Twitter account if applicable and to verify identity for saliva testing), and username and password for our website (and Twitter if applicable). In addition, they will be asked to supply additional names, phone numbers, and email addresses of collaterals which will only be used as last resorts to contact the participants. If the participant fails to provide the required personal information, s/he will be disqualified. Also an automated program will send both an email and a text to each participant and require a response to ensure both accounts are valid. If a participant fails, their photo will not be downloaded from the survey database. Those that pass will have their photographs used to verify identity during webcam interviews (for saliva tests). If the

participant is enrolled into a Twitter group, their photo will be used for their profile picture. After the study concludes, all copies of the pictures will be destroyed.

The screening survey will also ask about age, gender, marital status, years of education, race/ethnicity, employment status, years smoking, cigarettes per day, number of prior quit attempts, age when they started smoking, type of cigarettes they used, the Fagerstrom Test for Nicotine Dependence (FTND), and the Thoughts about Abstinence Scale^{103,104}. It will also assess use of other tobacco and ENDS (electronic nicotine delivery) products. It will assess social media use, and self-monitoring and self-disclosure as personality traits. The screening survey will also explain the study requirements to participants (e.g., the study may involve tweeting and receiving text messages on mobile phones daily, will involve taking surveys, etc.) and it will confirm that the participant understands and agrees to these study requirements.

If participants fail the screen, they will be thanked and referred to NCI's Smokefree.gov Quit Guide. No more communication will occur and they will be blocked to prevent re-attempts at enrolling. Their data will be kept for screening analyses, but not used as part of the study results.

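### Beyond gender (Aim 1) and cohort, no baseline covariate is fixed for the primary models; others enter only if dropout appears related to them, so smoking measures collected at screening may be omitted

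*SAP*

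**What the plan says.** The Aim 1 model is given in the SAP, Statistical Analyses: "Sustained abstinence will be modeled as a function of study arm (coed Tweet2Quit or control), gender, cohort, and individual using a logistic model", fitted by generalized estimating equations. The protocol (Section 6.A, Main Phase Randomized Controlled Trial) separately commits to gender, because the gender mix may differ between arms: "gender will be taken into account as a covariate during analysis". Aim 2 uses "The same type of generalized logistic model, but focusing on women".

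Other baseline measures are mentioned only in the SAP's opening paragraph, which deals with dropout and missing data. It says "Before analysis, we will examine baseline predictors of attrition", and then: "If it appears that attrition is related to measured aspects of the participants, we will include those measures as covariates in the models". It does not say how a relation is judged, which measures are candidates, or whether attrition means an unanswered survey, an unreturned saliva test, or both.

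The protocol's screening survey (Section 6.A, Enrollment Process) collects, among others, "years smoking, cigarettes per day, number of prior quit attempts, age when they started smoking", and also "the Fagerstrom Test for Nicotine Dependence (FTND), and the Thoughts about Abstinence Scale". None of these is named in an analysis model.

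**The concern.** A baseline covariate sharpens a treatment comparison when it predicts the outcome. Here a measure is admitted when it appears to predict dropout, which is a different property. A measure closely related to abstinence but unrelated to dropout would normally stay out.

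Three things follow:

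- Precision may be lost in both primary tests. Aim 2 is the more exposed: gender is constant among women, so that model has no fixed individual-level covariate at all.
- The covariate set is not settled until dropout has been observed. Two analysts could follow the text faithfully and fit different primary models.
- The odds ratio is not collapsible. Adding a prognostic covariate changes the quantity being estimated as well as its standard error, so the dropout pattern determines which odds ratio is reported.

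**Working it through.** **Inputs from the documents.** Aim 1 compares 480 coed-treatment participants with 240 controls, and Aim 2 compares 240 women with 240 women (protocol Section 1, aims). A coed cohort has 20 treated and 10 control participants, so Aim 1 has 480/20 = 24 cohorts. Aim 2 has 240/20 = 12 women-only cohorts. Expected survey response is 90% (Section 6.B). The text supplied gives no alpha, power, abstinence rates, intracluster correlation or prognostic strength for any covariate, so there is no stated power figure to reproduce. All rates and odds ratios below are assumptions.

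**Reference power, Aim 1, no covariate, no clustering, no attrition, two-sided 5%.** For 20% versus 30%:

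- pooled rate = (240×0.20 + 480×0.30)/720 = 0.267
- null SE = √[0.267×0.733×(1/240 + 1/480)] = 0.0350
- alternative SE = √[0.20×0.80/240 + 0.30×0.70/480] = 0.0332
- power = Φ[(0.10 − 1.96×0.0350)/0.0332] = Φ(0.947) ≈ 0.83

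The same formula gives 0.81 for 15% versus 24% and 0.82 for 10% versus 18%.

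**What the attrition rule does (Aim 1).** Simulated trials of 480 versus 240 used rates of 15% and 24%, with 10% attrition counted as smoking and no clustering. There were 2,000 runs per setting. The single covariate entered if it predicted attrition at p < 0.05; that threshold is assumed, because the SAP gives none. Attrition depended on the covariate but not on arm. For a covariate with odds ratio 2.0 per SD on abstinence:

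| Covariate's log-OR for attrition, per SD | Enters the model | Power: never / by rule / always adjusted | OR unadjusted / adjusted |
|---|---|---|---|
| 0 | 5.0% | 0.761 / 0.765 / 0.786 | 1.78 / 1.85 |
| 0.2 | 36.4% | 0.749 / 0.758 / 0.775 | 1.77 / 1.84 |
| 0.4 | 89.0% | 0.756 / 0.783 / 0.789 | 1.78 / 1.86 |

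At odds ratios of 1.3 and 1.6 the entry rates were nearly the same (4.0% to 5.2%, 35.1% to 36.8%, 88.2% to 88.4%). Entry therefore follows the link to dropout and not the link to abstinence. Across all nine settings, always adjusting gained between 0 and about 3 points over never adjusting.

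**Type I error.** With 15% in both arms (3,000 runs per setting), rejection under the rule was 0.046 to 0.052.

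**Gain with clustering, both aims.** Assumptions: 30% versus 20%, cohort random-effect SD 0.2 on the logit scale, cluster-robust variance with a t reference, one standard-normal covariate, and 2,000 runs per setting. Aim 2 used 12 women-only cohorts of 20 and 24 coed cohorts with 10 women each, with 5% of the covariate's variance between cohorts. Power without and with the covariate, from two separately coded runs:

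| Covariate OR per SD | Aim 1 | Aim 2 |
|---|---|---|
| 1.5 | 80→81%; 79→80% | 64→66%; 66→68% |
| 2.0 | 81→83%; 79→83% | 66→71%; 67→71% |
| 2.5 | 79→84%; 80→85% | 61→71%; 64→73% |

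A third run of the Aim 2 design gave gains of about 2.5, 6 and 7.5 points. The Monte Carlo standard error of one power estimate is about √(0.65×0.35/2000) = 0.011, so differences of a point or two between runs are noise.

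Ten women per coed cohort matches the 240 in the aims (24×10). The randomization text implies more: 20 treated with 4 to 8 men leaves 12 to 16 women. With 12 to 16, unadjusted Aim 2 power was about 66% to 74% and the gain from adjusting was similar.

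**The case against.** The strongest reply is that the quoted sentence is a missing-data rule. It sits between the examination of attrition predictors and the missing-data sensitivity analyses, and conditioning on predictors of dropout is a recognised way to make a missing-at-random assumption more plausible. Randomization makes the arm comparison valid without further covariates. This stands, and it means the sentence should be kept in some form. In the supplied text it is the only stated adjustment for covariate-dependent dropout, and there is no imputation model to move those predictors into. It does not answer the point that no other route exists for a baseline measure to enter the models.

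A reader might infer four stronger things that the documents do not support:

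- *That every covariate depends on dropout.* Gender is unconditional in Aim 1, and cohort is a named term.
- *That the model is tuned to the result.* Selection is placed before analysis and looks at dropout, not at abstinence by arm. The two are not wholly separate, because one planned analysis counts missing as smoking, but the simulation showed no excess of false positives.
- *That spurious selection is a serious harm.* Seventeen independent tests at 5% would flag at least one null measure with probability 1 − 0.95^17 = 0.58. However, the SAP states no 5% threshold, and independence is implausible (age, years smoking and age at starting are closely tied). An irrelevant covariate also does almost no damage to the arm comparison.
- *That FTND and cigarettes per day are known to be strong predictors.* The documents do not say so. The odds ratios used above are assumptions.

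**Conclusion.** The point holds as an avoidable gap in prespecification with a modest cost in precision. It is not a threat to validity.

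The gain from fixed adjustment is about 0 to 5 points of power for Aim 1: 0 to about 3 at 15% versus 24% with covariate odds ratios of 1.3 to 2.0, and 1 to 5 at 30% versus 20% with odds ratios of 1.5 to 2.5. For Aim 2 it is about 2 to 10 points at 30% versus 20% with odds ratios of 1.5 to 2.5. The upper ends need an odds ratio of 2.5 per SD, and the 10-point figure is partly simulation noise.

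All of this rests on assumed abstinence rates, cohort variation and prognostic strength. The finding on type I error rests on an assumed p < 0.05 version of the rule, no clustering, and attrition that does not depend on arm. The reported odds ratio would shift slightly with the covariate choice, for example about 1.78 against 1.85 at an odds ratio of 2.0 per SD.

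**What to change.** Before follow-up data are seen:

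- Name a short fixed covariate list, with functional form, for both primary models: gender for Aim 1; FTND, cigarettes per day and Thoughts about Abstinence score for both aims. The documents do not rank the screening measures, so the team may choose others, provided the list is fixed.
- Keep the attrition rule, but apply it as a sensitivity analysis that adds attrition-related baseline measures to the fixed model. State the candidate measures, the criterion, and what counts as attrition.
- Report the marginal (standardised) risk difference beside the adjusted odds ratio, and give the model without the added covariates as supportive.

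The data are already collected at screening, so the cost is SAP wording and a little programming. The one downside is that the adjusted odds ratio is conditional on the covariates, which is why the marginal risk difference should accompany it.

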Our first primary aim is to test the 6-month efficacy of Tweet2Quit with biochemical verification of abstinence. We hypothesize that relative to usual care (n=240), Tweet2Quit-coed groups (n=480) will achieve significantly greater bioconfirmed sustained abstinence out to 6-months follow-up.

Aim 2

Our second primary aim is to test whether women do better in Tweet2Quit women-only versus coed groups. We hypothesize that women in Tweet2Quit will achieve significantly greater bioconfirmed 6-month abstinence in woman-only groups (n=240) vs. coed groups (n=240 women in those groups).

Secondary Aims will test the same hypotheses, however, based on 3-month (end of treatment) sustained and bioconfirmed abstinence rates and we will also test 7-day point prevalence abstinence at 1, 3, and 6 months.

Exploratory Aims will study the Tweet2Quit groups' social network structures with a focus on the identification of buddy pairs and social brokers, both via baseline theoretically-based measures and observed tweeting behaviors. In particular, we will test the following conceptual models positing how dyadic tie strength and betweenness centrality may serve as mechanisms of effects and promote smoking abstinence.

- *Better matched buddy pairs based on demographics → dyadic tie strength → dyad abstinence.*
- *Better social brokers based on self-monitoring → betweenness centrality → group tweets → group abstinence.*
- *These links will be stronger for women in women-only groups vs. women in coed groups of Tweet2Quit.*

3. List up to **ten relevant references/articles** to support the rationale for the research.

1. Joinson A, N. "Looking at", "looking up" or "keeping up with" people? Motives and use of facebook. Proceedings of the SIGCHI Conference on Human Factors in Computing Systems; April 5-10, 2008, 2008; Florence, Italy.
4. Baumann P. *140 Health care uses for twitter.* 2009; <https://vpn.nacs.uci.edu/+CSCO+0h756767633A2F2F637576796F6E687A6E61612E70627A++/140-health-care-uses-for-twitter/>. Accessed January 16, 2009.

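### Aim 1 has no single fixed primary test: the outcome data decide whether the arm effect is tested overall or by gender, with no threshold, alpha or success rule given

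*SAP*

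**What the plan says.** Protocol Section 1.2 states Aim 1 as a single hypothesis: "relative to usual care (n=240), Tweet2Quit-coed groups (n=480) will achieve significantly greater bioconfirmed sustained abstinence". Protocol Section 6.A (Main Phase Randomized Controlled Trial) gives gender an adjustment role, because the gender ratio may differ between arms: "gender will be taken into account as a covariate during analysis".

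The SAP (Statistical Analyses) describes the Aim 1 outcome model as follows: "modeled as a function of study arm (coed Tweet2Quit or control), gender, cohort, and individual using a logistic model and generalized estimating equations". No arm-by-gender term is in that list. It continues: "We will test the coefficient of the study arm or treatment condition parameter", and then adds the condition "doing so by gender if there is a treatment condition by gender interaction". The secondary abstinence outcomes are to be analysed in the same way, so the condition carries over to those of their comparisons that include both genders.

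The available text gives no criterion for declaring an interaction, no significance level for any test, no division of alpha between genders, no rule on whether one or both genders must show a benefit, and no statement on whether the overall coefficient is still tested once the condition is met.

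**The concern.** A primary test should be identifiable before the outcomes are known. Here the abstinence data by arm and gender determine which test is run, and the result that counts as success in the gender-specific branch is left open.

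Each way of closing the gap has a cost. If a significant result in either gender is enough, a chance interaction gives the trial extra opportunities to claim success, and type I error rises. If both genders must be significant, error is controlled, but a real benefit shared by men and women is usually missed in those trials where an interaction appears by chance, because each gender-specific test has less power than the overall one. A reader of the final report could not tell which rule had been intended.

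**Working it through.** **Is there a figure to reproduce?** No. The available text gives no alpha, power, abstinence rates or sample-size calculation. The calculations below show how the written rule behaves under stated assumptions.

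**Inputs from the documents**
- Arm sizes: 480 coed treatment, 240 control (Section 1.2).
- Gender mix: 6-10 men per coed cohort of 30, with "a minimum of 4 men in coed tweet2quit" and an even number of each gender in the treated group (Section 6.A). Section 1.2, Aim 2, counts 240 women among the 480 treated, which is half. Men are therefore taken as 20% to 50%.
- Number of coed treatment groups: 480 / 20 = 24.

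**Assumptions**
- Each efficacy test is two-sided at 5%.
- The interaction is declared at a threshold of 1%, 5%, 10% or 20%.
- Cohort clustering is ignored.

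**Step 1: type I error, no effect in either gender.** Let z_F and z_M be independent standard normal statistics for women and men, and w the women's share of the information.
- Overall: z_O = √w·z_F + √(1−w)·z_M
- Interaction: z_I = √(1−w)·z_F − √w·z_M
- Rule: if z_I is significant, test each gender at |z| > 1.96; otherwise test |z_O| > 1.96.

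Results from 4,000,000 draws, as the range over men's share:

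| Interaction threshold | Either gender suffices | Both required |
|---|---|---|
| 1% | 5.9-6.0% | – |
| 5% | 8.0-8.3% | 4.9% |
| 10% | 9.4-9.6% | 4.6% |
| 20% | 10.6-10.8% | – |

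Counting only false claims of benefit under the either rule, the error rises from 2.5% to 4.1-4.2% at a 5% threshold.

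**Step 2: check with binomial data at 480 versus 240.** Gender-stratified log odds ratios were used, with equal abstinence of 10-30% in both arms. The either rule with a 5% threshold gives 6.5-8.2%, against 4.4-4.9% for the overall test alone.

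**Step 3: power if both genders are required.** With a true 30% versus 20% in each gender, the overall test in the same simulation has 82% power.
- 5% threshold: power is 78-79%. A chance interaction arises in under 5% of trials, and about 2-13% of those trials then succeed. That range moves by a point or two with the handling of small cells.
- 10% threshold: power is 75-76%.

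**Step 4: power of the single-gender tests.** With the Section 6.A quotas, randomly drawing 20 of 30 subject to the restrictions on men gives on average 103 treated men (6 per cohort) to 160 (10 per cohort).
- Control men: 24×6 − 103 = 41, to 24×10 − 160 = 80.
- Treated women: 480 − 160 = 320, to 480 − 103 = 377.
- Control women: 240 − 80 = 160, to 240 − 41 = 199.

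Unpooled formula: power = Φ(δ/SE − 1.96), with SE = √(p₀(1−p₀)/n₀ + p₁(1−p₁)/n₁).
- Overall, 30% v 20%: SE = √(0.16/240 + 0.21/480) = 0.0332; 0.10/0.0332 − 1.96 = 1.05; power 85%.
- Men, smallest case: SE = √(0.16/41 + 0.21/103) = 0.0771; 0.10/0.0771 − 1.96 = −0.66; power 25%.

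The ranges below also include the pooled-variance formula, which is lower:

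| Test | 30% v 20% | 20% v 10% |
|---|---|---|
| Overall, 480 v 240 | 83-85% | 94-96% |
| Women, Section 6.A quotas | 65-77% | 82-92% |
| Men, Section 6.A quotas | 21-41% | 28-58% |
| Either gender, 240 v 120 | 53-57% | 69-76% |

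The last row assumes the control arm has the same half-and-half mix as Aim 2 implies for the treated arm. The overall figure here is slightly above the 82% in Step 3 because the formulas compare proportions, while the simulation tests a gender-stratified log odds ratio.

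**Step 5: does splitting alpha repair it?** Not fully. Testing each gender at 2.5% only in the interaction branch, under the either rule, still gives about 6.9-7.1% (5% threshold), 7.5% (10%) and 7.5-7.8% (20%).

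**The case against.** The strongest reply is that the SAP never says a result in one gender is enough. Aim 1 is a single coed-versus-control hypothesis, so the inflated figures rest on a rule the plan does not contain. That is right as far as it goes: what is established is an undefined decision rule, and inflation follows only under one way of defining it.

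A second reply is that the clause may mean ordinary follow-up of an interaction, with gender-specific tests added to the overall test. This does not remove the problem. By the definitions in Step 1, z_O² + z_I² = z_F² + z_M². With a 5% threshold, if the overall and interaction statistics both exceed 1.96, the sum exceeds 2 × 3.84 = 7.68, so at least one gender statistic must also exceed 1.96. Keeping the overall test alongside therefore gives the same error rate under the either rule.

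Other points are fair but limited. The protocol's covariate statement does not exclude an interaction analysis. The loss under the both rule is only 3-4 percentage points at a 5% threshold, because chance interactions are uncommon. The error depends on assumed inputs and is smaller when abstinence is low: at 5% abstinence in both arms, the either rule with a 5% threshold gives only 5.2-5.4%. The single-gender powers assume equal effects in both genders. Finally, part of the SAP was not in the text available, so the absence of a threshold or alpha can be asserted only for that text; the conditional clause itself is in it.

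**Conclusion.** The concern holds and should be fixed. The clause lets outcome data select the Aim 1 primary test, and the available text does not define how success is then judged. That conclusion needs no assumed number.

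The consequence is moderate. It is either a type I error of roughly 6-11% in place of 5%, over interaction thresholds of 1-20% in the normal approximation, or no inflation with a power loss of about 3-4 points (5% threshold) to 6-7 points (10% threshold). Which applies depends on the rule chosen. All these figures assume two-sided 5% tests and no clustering.

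**What to change.** Delete the conditional clause and state in the SAP that the gender-adjusted study-arm coefficient, estimated in all coed-treatment and control participants, is the only Aim 1 primary test, at a stated alpha, whatever the interaction shows. Add that the arm-by-gender interaction and the gender-specific estimates with confidence intervals will always be reported as secondary results. Under the assumptions above this returns the Aim 1 error to 5%, and it matches the hypothesis in Protocol Section 1.2.

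Defining a threshold and a success rule while keeping the switch would remove the ambiguity, but would still leave either inflated error or lost power.

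The cost is one SAP sentence, with no new data or participants. The downside is that a gender-specific finding could no longer be claimed as the primary result.
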